### **8.3 Definition of Baseline**

Baseline is defined as the last measurement prior to the administration of study medication. Change from baseline will be calculated as post-baseline visit minus baseline visit.

### **8.4 Data Analysis Conventions**

The final data analysis will be performed by SDC after the study is completed and the database has been locked. Statistical programming and analyses will be performed using SAS® Version 9.4 or higher. Output will be provided in rich text format (RTF) for tables and portable document format (PDF) for tables, listings, and figures using landscape orientation. All study data will be listed by subject, treatment, and visit (as applicable).

Summaries for continuous and ordinal variables will include the number of observations (n), arithmetic mean, standard deviation (SD), median, minimum, and maximum. Minima and maxima will be reported with the same precision as the raw values; means and medians will be presented to one additional decimal place than reported in the raw values. Standard deviations will be presented to two additional decimal places than reported in the raw values. Summaries for discrete variables will include number of observations, and percentages. All percentages will be rounded to one decimal place (i.e., XX.X%). Unless otherwise specified, summaries will be presented by cohort and, where appropriate, visit.

## 8.5 Adjustments for Multiplicity

No statistical adjustments for multiplicity are planned due to the exploratory nature of this study.

## 9. Disposition of Subjects

Subject disposition will be presented in terms of the numbers and percentages of subjects who completed the study and discontinued from the study. Subjects who are not discontinued from the study will be considered study completers. Disposition will be summarized by cohort and for total subjects. The number of subjects in each of the analysis sets (FAS, PP, and SS) will be displayed by cohort total subjects. Percentages will be calculated using enrolled subjects as the denominator.

The number and percentage of subjects enrolled, and failed screening will be presented using total number of subjects screened as denominator. Reasons for screen failures would include number and percentage of subjects who either failed to meet inclusion criteria or met exclusion criteria.

The number and percentage of subjects prematurely discontinued from the study and the reasons for study discontinuation will be summarized by cohort for all enrolled subjects. The reasons for study discontinuation that will be summarized include withdrawal of consent, lost to follow-up, adverse event, sponsor termination of study, and other. A subject listing will be provided that includes the date of and reason for premature study discontinuation.

The number and percentage of subjects with major protocol deviations will be summarized by cohort and total enrolled subjects. The protocol deviations that will be summarized include: informed consent, inclusion/exclusion or treatment assignment, test article/study drug administration at site, improper protocol procedures at site, site's failure to report SAE, visit out of window, subject's use of prohibited concomitant medication, subject's failure to follow instructions, and other. A subject listing will be provided that includes the start and end date of the deviation, the deviation code, the deviation description, and the classification of whether the deviation was judged to be major or minor.

In addition, subject listings will be provided that include informed consent date, inclusion and exclusion criteria violations, and exclusions from the Per Protocol Analysis Set.

## 10. Demographic Variables and Pretreatment Variables

### 10.1 Demographic Variables

The demographic variables collected in this study include age, sex, race, ethnicity, and iris color of study eye. Demographic variables will be summarized for the FAS, PP and Safety analysis sets, separately. Subjects who report more than one race will be summarized in the Multiple Race category. Age will also be categorized as follows: < 65 and  $\geq$  65 years. Age will be reported in years and calculated using the following formula:

$$\text{Age} = (\text{Informed Consent Date} - \text{Date of Birth}) / 365.25, \text{ truncated as an integer}$$

The number and percentage of subjects will be presented, overall and by cohort, for age, sex, race, ethnicity, and iris color for the study eye.

A subject listing that includes all demographic variables will be provided.

## **10.2 Pretreatment Variables and Anti-VEGF History**

Pretreatment variables will include baseline BCVA and CST in the study eye. Baseline BCVA, and baseline CST will be summarized, total and by cohort, using continuous descriptive statistics. Additionally, all two pretreatment variables will be categorized as follows: SD-OCT ( $\leq 350$  and  $> 350$  micrometers), and BCVA ( $\leq 68$  versus  $> 68$  letters).

Anti-VEGF history will include previous number of Anti-VEGF injections, time (in months) since first anti-VEGF and last anti-VEGF. Number of injections will be summarized as categorical variable ( $< 5$  versus  $\geq 5$ ) and time since first and last injections will be summarized as continuous variables. All the summaries will be presented, total and by cohort.

Subject listings including all pretreatment variables and Anti-VEGF history will be provided.

## **11. Medical History and Concomitant Medications**

### **11.1 Medical History**

Medical history will be coded using the medical dictionary for regulatory activities (MedDRA) version 22.0. Non-ocular medical history will be summarized using discrete summary statistics and presented by cohort at the subject and event level by System Organ Class (SOC) and Preferred Term (PT) using the SS. Ocular medical history will be similarly summarized at the subject level by study and non-study eye. If a subject reports the same PT multiple times within the same SOC, that PT will only be reported once within that SOC. As with the PT, if a subject reports multiple conditions within the same SOC, that SOC will only be reported once. SOCs and PTs will be listed in alphabetical order.

Listings of medical history will be generated separately for ocular and non-ocular data.

### **11.2 Prior and Concomitant Medications**

Prior and concomitant medications will be coded using the World Health Organization Drug Dictionary (WHODrug) Global (B3, March 2019) and summarized to the therapeutic drug class (Anatomical Therapeutic Chemical [ATC] 4 classification) and preferred name. If the ATC 4 classification is not provided, the next lowest classification that is provided in the coding dictionary will be used. The preferred name will be defined as the active ingredient; if the active ingredient is not provided or includes more than two ingredients (e.g., multivitamins), then the drug name will be summarized as the preferred name. Any uncoded terms will be summarized under the ATC classification and preferred name of "Uncoded." Prior medications are defined as those medications listed as having stopped prior to initiation of study drug. Concomitant medications are defined as those medications listed as having been taken: (1) prior to initiation of study drug and continuing for any period of time following the first administration of study drug, or (2) at

any time following the first administration of study drug. Prior medications are defined as medications initiated prior to study drug Administration including both those stopped before baseline and those continued after baseline.

Prior and Concomitant medications will be summarized for ocular and non-ocular medications separately using the SS. All the ocular events will also be further summarized by study and non-study eye. Medications will be tabulated for each cohort using frequencies and percentages. Subjects may have more than 1 medication per ATC text. At each level of subject summarization, a subject will be counted once if 1 or more medications is reported. Percentages will be based on the number of subjects in each cohort. ATC classes and preferred names within an ATC class are listed in alphabetical order.

Listings of prior and concomitant medications and procedures will be generated separately for ocular and non-ocular data.

### **11.3 Study Drug Administration**

Descriptive summary statistics of study drug administration will be tabulated by each cohort. Variables like study eye (OD/OS), drug administration performed as per pharmacy manual (Yes/No), completion of post-injection assessment (Yes/no) will be included in the analysis.

A subject listing of study drug administration will be generated.

### **12. Pharmacodynamic Analysis**

BCVA, CST (using SD-OCT), and rescue treatment (time to first rescue treatment, number of rescue treatments) will be included as pharmacodynamic endpoints. No formal hypothesis testing will be conducted. Descriptive summaries will include the arithmetic mean, SD, median, minimum, and maximum values for continuous variable, and the number of subjects and percentages for categorical variable.

Observed data will contain assessments performed during protocol defined and unscheduled visits including ones performed after the first rescue treatment. To allow for an efficacy assessment of GB-102 while excluding potential effects from rescue injections data collected after first rescue treatment will be censored and replaced with the last value collected prior to the first rescue treatment. The LOCF approach is used for the analysis of BCVA and CST.

Sensitivity analysis will also be conducted using observed data without any censoring and imputation as mentioned in the previous paragraph.

The response to anti-VEGF rescue treatment is assessed for BCVA and CST based on the data collected prior and after the first rescue treatment. This response analysis will include all subjects receiving at least one rescue treatment. The last assessment performed before receiving the first rescue treatment will be used as the rescue treatment related baseline value. Data from one month and two months prior to the rescue treatment - baseline as well as one and two months post rescue treatment will be used to assess

the response to rescue treatment. These five timepoints will represent the time-scale for these analyses. No imputation for missing data will be done.

Summaries will be produced for the overall as well as by diagnosis (DME or RVO) within FAS and PP analysis set.

All observed pharmacodynamic variables will also be presented by visit in subject listings.

## 12.1 BCVA

Visual acuity assessment (BCVA) using ETDRS protocol with manifest refraction will be performed in both eyes at all visits. The number of letters read correctly in the study eye will be the BCVA endpoint.

### 12.1.1 LOCF AND OBSERVED DATA APPROACH

Values and change from baseline in number of letters read correctly will be summarized using LOCF approach for study eye by visit and cohort using continuous descriptive statistics. Categorical change from baseline will also be summarized for study eye by visit, total and by cohort.

Observed values and change from baseline in number of letters read correctly will be summarized for study eye by visit and cohort using continuous descriptive statistics. Categorical changes from baseline will also be summarized for study eye by visit, total and by cohort.

### 12.1.2 RESPONSE TO FIRST RESCUE TREATMENT ANALYSIS

For the subset of subjects with at least one rescue treatment the observed and change from rescue treatment baseline in number of letters read correctly will be summarized for study eye by time-point and cohort using continuous descriptive statistics.

## 12.2 CST (spectral-domain optical coherence tomography [SD-OCT])

The SD-OCT imaging will be performed for both eyes to measure and assess cross-sectional images of the anatomic layers of the retina and to detect the presence of retinal fluid. Images will be obtained using a SD-OCT device by designated certified study center personnel. Preferably the same device will be used for screening and the subsequent follow-up assessments for each subject. Images will be read centrally, and CST measurement data provided to SDC.

### 12.2.1 LAST OBSERVATION CARRIED FORWARD AND OBSERVED DATA APPROACH

Values and change from baseline in CST measurements will be summarized using LOCF approach for study eye by visit and cohort using continuous descriptive statistics. Categorical change from baseline will also be summarized for study eye by visit, total and by cohort.

Observed values and change from baseline in CST measurements will be summarized for study eye by visit and cohort using continuous. Categorical changes from baseline will also be summarized for study eye by visit, total and by cohort.

### 12.2.2 RESPONSE TO FIRST RESCUE TREATMENT ANALYSIS

For the subset of subjects with at least one rescue treatment the observed and change from rescue treatment baseline in number of letters read correctly will be summarized for study eye by time-point and cohort using continuous descriptive statistics.

### 12.3 Rescue-free treatment

Rescue treatment (any anti-VEGF agent; afibercept, bevacizumab, or ranibizumab) for all subjects enrolled is allowed at any visit following the Day 30 study assessments in subjects who meet any of the following criteria regarding decrease in BCVA and/or increase in CST:

Decrease in BCVA:

- $\geq 10$  ETDRS letter decrease compared with best on-study (i.e., post-treatment) BCVA ETDRS letter score

Increase in CST (any of the following criteria)

- $\geq 75$   $\mu\text{m}$  compared with the average of the last 2 on-study (i.e., post-treatment) visit CST measurements ( $\mu\text{m}$ ), and/or,
- $\geq 100$   $\mu\text{m}$  compared with the lowest on-study (i.e., post-treatment) CST measurement ( $\mu\text{m}$ )

Subjects may receive rescue treatment during a scheduled or unscheduled visit. Rescue treatment received during an unscheduled visit will be counted towards next scheduled visit.

Time to first rescue treatment including median time to first rescue treatment will be assessed using Kaplan-Meier product-limit approach by cohort. Subjects will be considered to have an event at the date where rescue treatment for study eye was first initiated. Since rescue treatment may be initiated at any time – at a scheduled visit or between scheduled visits – the timing of rescue treatment usage will be based on the date in at which rescue treatment was started. Subjects who do not have any usage of rescue treatment in the study eye will be censored at the date of the last visit. Subjects who discontinue prior to completing all treatment period visits will be evaluated based on the visits which are available. Kaplan-Meier plots will be generated.

For the subgroup of subjects with rescue treatment the time to first rescue treatment will be summarized by cohort using continuous descriptive statistics.

Proportion of subjects receiving rescue treatment during any protocol defined visit will be tabulated by cohort. As subjects will be eligible to receive rescue treatment on or after Day 30, Month 1 will be the first visit to be included in this table.

A contingency table will be generated to represent a cross-classification between whether rescue criteria were met (yes or no) versus received rescue treatment (yes or no). Contingency will be checked across all visits as well as at every visit starting from Month 1.

The total number of rescue treatments received by each subject will be tabulated.

Rescue treatment will be listed by subject and medication.

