Pharmacodynamic activity will be assessed by means of BCVA (using the ETDRS Protocol), retinal central subfield thickness (CST) using spectral-domain optical coherence tomography (SD-OCT), and color fundus photography (CFP) (including wide field fundus photography, if available).

Safety Monitoring

The medical monitor will evaluate the on-going open-label safety data.

Masking

This is an open-label study and the injecting investigator/physician may be the assessing investigator. The SD-OCT and CFP technicians and other site personnel, the Sponsor, and CRO are unmasked to treatment assignment.

Rescue Treatment

Rescue treatment (any anti-VEGF agent; aflibercept, bevacizumab, or ranibizumab) will be permitted in the study eye in **any** of the study arms if the qualifying criteria are met for rescue treatment.

Study Eye
Determination:

The **study eye** is defined as the eye that meets all the inclusion criteria and none of the exclusion criteria. If both eyes meet the inclusion and none of the exclusion criteria, the eye with the worst visual acuity at baseline will be selected. If both eyes have the same baseline visual acuity, the right eye will be selected as the **study eye**.

Rescue Treatment
Criteria:

Rescue treatment (any anti-VEGF agent; aflibercept, bevacizumab, or ranibizumab) for all subjects enrolled is allowed at any visit following the Day 30 study assessments in subjects who meet any of the following criteria regarding decrease in BCVA and/or increase in CST:

Decrease in BCVA:

- ≥ 10 ETDRS letter decrease compared with best on-study (i.e., post-treatment) BCVA ETDRS letter score

Increase in CST (any of the following criteria):

- ≥ 75 μm compared with the average of the last 2 on-study (i.e., post-treatment) visit CST measurements (μm), and/or,

- $\geq 100 \mu\text{m}$ compared with the lowest on-study (i.e., post-treatment) CST measurement (μm)

The investigator may elect to withhold rescue treatment if, in the opinion of the investigator, further clinical monitoring is warranted (e.g., subject has difficulty reading eye chart due to seasonal allergies and experiences a decline in BCVA but the OCT imaging shows no evidence of fluid).

Rescued subjects will remain in the study for continued scheduled follow-up observation.

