6.2.4 Month 6 (Day 180 ± 7) / Early Termination

The following procedures are to be performed:

- Review concomitant medications and procedures
- Query for AEs
- Conduct a physical examination
- Conduct a urine pregnancy test on women of childbearing potential
- Obtain vital signs (blood pressure, heart rate and weight)
- Assess BCVA (using the ETDRS protocol with manifest refraction) in both eyes
- Perform the slit-lamp biomicroscopy of both eyes
- Measure IOP (via Goldmann applanation tonometry or Tono-Pen) in both eyes
- Perform dilated ophthalmoscopy of both eyes
- Obtain SD-OCT imaging of both eyes
- Perform CFP in the study eye to document the position of the depot and the status of the visual axis
- Exit the subject from the study

If follow-up is needed after the early termination visit, it should occur as a poststudy, unscheduled visit at the discretion of the investigator.

Subjects with an ongoing SAE at this visit should be followed until the event resolves or stabilizes as described in [Section 8.8](#).

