#### 4. Study Design and Procedures

##### 4.1 General Study Design

This is a Phase 2a, multicenter, open-label, single injection, parallel arm, non-controlled safety, tolerability, and pharmacodynamics study. Eligible subjects will be enrolled to 1 of 2 concurrently initiated open-label GB-102 treatment arms: Group 1: 1 mg (50 µL) and Group 2: 2 mg (50 µL). Subjects will receive the IVT injection of the study drug in the study eye on Day 1.

The planned study assessments (AEs including SAEs, physical examinations, vital signs, BCVA using the ETDRS protocol, slit-lamp biomicroscopy findings, IOP measurements, dilated ophthalmoscopy results, and date of administration of rescue treatment) are conventional parameters used to evaluate the safety of pharmacologic agents in retinal disease. Approximately 20 subjects are planned: 10 subjects treated with 1 mg GB-102 and 10 subjects treated with 2 mg GB-102. There is no pre-set limitation on the proportion of diabetic macular edema (DME) or RVO subjects per dose group. Rescue treatment allowed is any anti-VEGF (aflibercept, bevacizumab, or ranibizumab) and should be used in accordance with the sites standard practice in administering these agents for the treatment of DME or RVO.

Pharmacodynamic activity will be assessed by means of BCVA (using the ETDRS Protocol), retinal CST using SD-OCT, and CFP (including wide field fundus photography, if available).

The null and alternative hypotheses, based on the primary variables, are as follows:

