##### 4.2 Schedule of Visits and Assessments

GB-102 will be administered on Day 1 in both Cohorts. Subjects will return to the study center on Days 14, 30, 60, 90, 120, 150, and 180 for safety and clinical assessments. Subjects will exit the study following all study assessments on Day 180.

The schedule of visits and assessments is provided in Table 1 below.

Table 1. Study Plan and Schedule of Assessments

| Activity/Assessment                         | S a | B              | W 2  | M 1  | M 2  | M 3  | M 4   | M 5   | M 6 (ET) |
|---|----------------|----------------|------|------|------|------|-------|-------|----------|
| Visit Day ± Window b             | -30 to -3      | 1              | 14±2 | 30±4 | 60±7 | 90±7 | 120±7 | 150±7 | 180±7    |
| Informed Consent/HIPAA                      | X              |                |      |      |      |      |       |       |          |
| Inclusion/Exclusion Criteria                | X              |                |      |      |      |      |       |       |          |
| Demographics Data                           | X              |                |      |      |      |      |       |       |          |
| Medical/Medication History                  | X              |                |      |      |      |      |       |       |          |
| Physical Examination                        | X              |                |      |      |      |      |       |       | X        |
| Pregnancy Testing c              | X              | X              |      |      |      | X    |       |       | X        |
| Clinical Laboratory Tests d      | X              |                |      |      |      |      |       |       |          |
| Adverse Events                              | X              | X e | X    | X    | X    | X    | X     | X     | X        |
| Concomitant Medications                     | X              | X              | X    | X    | X    | X    | X     | X     | X        |
| Vital Signs f                    | X              | X              |      |      |      |      |       |       | X        |
| BCVA (ETDRS) g                   | OU             | OU             | OU   | OU   | OU   | OU   | OU    | OU    | OU       |
| Slit-lamp Biomicroscopy                     | OU             | OU             | OU   | OU   | OU   | OU   | OU    | OU    | OU       |

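### With actual-date censoring across a 15-day exit window, the end of the time-to-rescue Kaplan-Meier curve falls below the proportion never rescued whenever a Month 6 rescue follows another unrescued subject's exit

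*SAP*

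**What the plan says.** SAP section 12.3 sets the method: "Time to first rescue treatment including median time to first rescue treatment will be assessed using Kaplan-Meier product-limit approach by cohort". For events, "the timing of rescue treatment usage will be based on the date in at which rescue treatment was started". For subjects without an event, "Subjects who do not have any usage of rescue treatment in the study eye will be censored at the date of the last visit". Neither that section nor the rest of the SAP has a nominal-day or windowing rule for this analysis.

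The last visit is headed "Month 6 (Day 180 ± 7) / Early Termination" in Protocol section 6.2.4, which gives Day 173 to Day 187. SAP section 4.2 adds: "Subjects will exit the study following all study assessments on Day 180". On timing, SAP section 12.3 states that rescue "is allowed at any visit following the Day 30 study assessments in subjects who meet any of the following criteria", and the Protocol synopsis and section 5.6.1 agree. Month 6 is therefore not excluded, although the Month 6 procedures list no rescue step and end with the subject leaving the study.

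SAP section 4.1 plans "10 subjects treated with 1 mg GB-102 and 10 subjects treated with 2 mg GB-102". Time to first rescue is part of the secondary objective and is listed as a secondary endpoint in SAP section 3. Table 14.2.3.1, the Kaplan-Meier table, is in bold in SAP section 15, the marking for topline output. Kaplan-Meier curves are the only figures planned in SAP section 17.

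**The concern.** Each completer who reaches Month 6 unrescued has one last assessment, after which the eye is either rescued (an event) or leaves (censored). Both happen on that subject's own visit date. Kaplan-Meier assumes that a censored subject still faces the risk borne by those who remain. An eye seen on Day 174 and not rescued no longer does, because it has already passed the Month 6 decision. If another eye is rescued on Day 186, that event is divided by a risk set emptied only by the booking calendar.

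The same clinical outcomes can then give different ends to the curve. With 10 per dose, and fewer in the curves by diagnosis, one late-booked rescue can pull a curve to zero or create an apparent dose difference. The study is descriptive, so the curve itself is the result, and nothing downstream would correct it.

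**Working it through.** **Inputs from the documents.** Actual-date events and censoring (SAP 12.3); Month 6 at Day 173 to 187 (Protocol 6.2.4); Month 5 at Day 143 to 157 (150 ± 7, schedule of assessments), so the two windows do not overlap; 10 subjects per dose (SAP 4.1). The documents state no rescue rate, median or rescue-free figure, so there is no plan figure to reproduce.

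**Where the problem can arise.** Without withdrawals nobody is censored before Day 173, so the curve through Month 5 is unaffected. Only at Month 6 do events and administrative censoring mix.

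**One Month 6 rescue.** Let m unrescued eyes attend Month 6 on distinct days, and let the rescued eye be seen j-th. The final factor is 1 − 1/(m − j + 1). The factor that matches the proportion rescued is 1 − 1/m. The first never exceeds the second, so the error goes only downwards.

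Take 10 eyes, 3 rescued earlier (curve at 0.70), m = 7 and one rescue at Month 6. The proportion never rescued is 6/10 = 60%.

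| Rescued eye seen | End of curve |
|---|---|
| 1st | 0.70 × 6/7 = 60% |
| 4th | 0.70 × 3/4 = 52.5% |
| 5th | 0.70 × 2/3 = 46.7% |
| 6th | 0.70 × 1/2 = 35% |
| 7th | 0.70 × 0 = 0% |

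**Average over booking order.** If each of m eyes is rescued at Month 6 with probability p and dates are distinct, the expected factor is the product over k = 1 to m of (1 − p/k), against a true 1 − p. For m = 7 and p = 1/7 this is 0.679 against 0.857. After the 0.70 it is 0.475 against 0.60.

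**Size at a constant rate per visit.** Simulation with 10 per cohort, rescue possible at Months 1 to 6, whole-day dates uniform in each window, events before censorings on tied days, no withdrawals and 20,000 trials. The rates are assumptions.

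| Rate per visit | Mean bias at end of curve (points) | Cohorts where the median moves from not reached into Day 173–187 |
|---|---|---|
| 3% | −3.8 | 5.3% |
| 5% | −5.3 | 8.1% |
| 10% | −6.7 | 6.0% |
| 15% | −5.9 | 1.8% |
| 20% | −4.6 | 0.3% |
| 25% | −3.1 | about 0% |

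The end of the curve was below the crude proportion in 20% to 38% of cohorts and never above it. It fell to zero while some subjects were unrescued in 2% to 15%. Normally distributed dates (SD 3 days) at 10% give −6.4 points instead of −6.7. With the Month 6 rate set to zero the bias is exactly zero.

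**Size with more rescue at Month 6.** With 30% rescued earlier and p = 0.10, 1/7 or 0.20 at Month 6, the mean bias is about 8, 11 and 14 points. At p = 1/7 the error is at least 10 points in 35% of trials.

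**Median.** If the curve reaches 50% before Day 173, Month 6 censoring cannot alter the median. If the curve is still above 50%, it can. In the first table the median is not reached when the rescued eye is seen fourth or earlier (at least 52.5%), but is reported inside the window when it is seen fifth or later (46.7% or less).

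**The case against.** The strongest reply is that this depends on a rescue at the exit visit. The documents permit one but describe no such step at Month 6. If none occurs, there is no bias. That stands, and the point is conditional on it.

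Second, a reader might infer that the median is biased low in general. The documents do not support this. A median reached before Day 173 is untouched, and at constant rates a falsely reached median occurs in 0% to about 8% of cohorts.

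Third, a reader might take 8 to 14 points as the expected size. Having 30% rescued over Months 1 to 5 implies 1 − 0.70^(1/5) = 6.9% per visit, so 10% to 20% at Month 6 assumes a rise at exit. With 6.9% at Month 6 the mean bias is about 6 points.

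Fourth, an unaffected companion exists. Table 14.2.4.1, also in bold, tabulates rescue by scheduled visit, the endpoint of subjects rescue-free at each visit does not use these dates, and the SAP names no Month 6 Kaplan-Meier landmark. This limits the harm, but the time-to-event table and all planned figures still carry the error and could disagree with that table without explanation.

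Finally, the standard error of a 60% proportion with 10 subjects is √(0.6 × 0.4/10) = 15.5 points, larger than the bias, and censoring at the last visit is a common convention. Both are true. But the bias has one direction, comes from a rule and can be removed, whereas sampling error cannot.

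**Conclusion.** The point holds in a limited form. If any eye is rescued at Month 6 after another unrescued completer has exited, the end of the curve falls below the proportion never rescued, and by how much depends on booking order. The mean bias is about 3 to 7 points at constant rates of 3% to 25% per visit, and about 8 to 14 points if 30% are rescued earlier and 10% to 20% of the rest at Month 6. A single cohort can be much further out, as the 60% to 0% example shows.

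These sizes assume the stated rescue rates (the documents give none), no withdrawals, and visit days unrelated to the need for rescue. The existence and direction of the error follow from the date rules alone. The documents do not support a claim that the bias is certain, or that the median is generally too low. Severity is minor to moderate, in a descriptive secondary analysis without hypothesis tests.

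**What to change.** In SAP section 12.3, keep actual dates for rescue events, but censor unrescued subjects who complete Month 6 at the end of the window (Day 187, or the latest Month 6 visit if later), with events before censorings at ties. Subjects who withdraw early stay censored at their actual last visit. In the example the Month 6 factor is then 6/7 whatever the booking order, and the curve ends at 60%. Without withdrawals the end value equals the proportion never rescued.

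Alternatively, put all events and censorings on nominal visit days, events first, and assign unscheduled rescues to the next scheduled visit, as section 12.3 already does for its visit counts. In simulation this gives a mean of 0.531 against a true 0.531 at 10% per visit. Moving only scheduled-visit dates is not enough. With 3 earlier rescues, 6 exits placed on Day 180 and an unscheduled rescue on Day 183, the curve falls to 0% although 60% were never rescued.

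A standard actuarial life table is not a substitute. It counts half of those censored as at risk, so the risk set is 7 − 6/2 = 4 and the end value 0.70 × 3/4 = 52.5%.

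Show the crude Month 6 rescue-free proportion (the complement of cumulative rescue) beside the curve, and state whether a rescue given at the exit visit counts as an event.

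The cost is one sentence and one derived variable. The first option credits completers with up to two weeks of nominal follow-up; the second loses day detail within windows. Actual dates can remain in the listings.
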